### 3.4.2 Exclusion Criteria

Subjects who meet any of the following criteria cannot be enrolled:

1. Previous pneumococcal disease (either confirmed or by self-reporting).
2. Previous receipt of a licensed or investigational pneumococcal vaccine.
3. Receipt of any investigational study product within 30 days prior to enrollment into the study, currently participating in another interventional investigational study, or having plans to receive another investigational product(s) while on study.
4. Planned or actual administration of any licensed vaccine during the period starting 30 days before enrollment into the study through Day 29.
5. Physical examination indicating any clinically significant medical condition.
6. Body Temperature  $> 38.0^{\circ}\text{C}$  ( $> 100.4^{\circ}\text{F}$ ) or acute illness within 3 days prior to study vaccination (subject may be rescheduled).
7. Seropositive to HIV, HCV, or HBsAg.
8. History of severe allergic reaction with generalized urticaria, angioedema, or anaphylaxis.
9. Female who is breast-feeding or planning to become pregnant during study participation.
10. Bleeding disorder diagnosed by a doctor (eg, factor deficiency, coagulopathy, or platelet disorder requiring special precautions) or significant bruising or bleeding difficulties with IM injections or blood draws.
11. Any other chronic or clinically significant medical condition that, in the opinion of the investigator, would jeopardize the safety or rights of the subject or confound evaluation of the study vaccine, including but not limited to: diabetes mellitus type I, untreated hypertension, chronic hepatitis; or clinically significant forms of: drug or alcohol abuse, asthma, autoimmune disease, psychiatric disorders, heart disease, pulmonary disease, neurologic disease, cancer, or any known or suspected impairment immune function.
12. Any medical, psychiatric, or social condition that, in the judgment of the investigator, is a contraindication to protocol participation or impairs a subject's ability to give informed consent.
13. Received blood or blood product (including Immune Globulin IV) within 90 days prior to enrollment into the study.
14. Received systemic corticosteroids for  $\geq 14$  consecutive days and has not completed treatment  $\leq 30$  days prior to enrollment into the study.

15. Receiving immunosuppressive therapy, including chemotherapeutic agents used to treat cancer or other conditions, immunostimulants, and treatments associated with organ or bone marrow transplantation, or autoimmune disease.
16. History of malignancy  $\leq$ 5 years before enrollment, except for adequately treated basal cell or squamous cell skin cancer or in situ cervical cancer.

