### 3.2 Number of Study Participants

The study population will be composed of at least 864 healthy US adults who meet the eligibility criteria listed in [Section 3.4](#).

Approximately 64 eligible subjects aged 18 to 49 and 800 subjects aged 50 to 64 years will be enrolled.

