#### Re-screening

A subject who meets exclusion criterion of having a current acute febrile illness at the time of scheduled enrollment may be re-screened after resolution of the acute illness. A subject who meets exclusion criteria of taking an investigational product, licensed vaccines, or medications (ie, systemic corticosteroid) within 30 days (or blood or blood product within 90 days) prior to Day 1 may be re-screened after the appropriate duration has passed. If an eligible subject is not able to be randomized and treated within 30 days of the Screening period, all screening procedures must be conducted again, including re-consenting and use of a new subject ID number. A subject may be re-screened one time only. Re-screening is not otherwise permitted.

If a subject is re-screened, a new subject number will be assigned as they are entered into the EDC for a new Screening visit and the previous subject number will be captured in the source file of the newly assigned subject number.

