## **5.14 Prohibited Medications and Therapies**

Subjects must not have received or be planning to receive:

- Licensed or investigational pneumococcal (pneumonia) vaccine.
- Investigational agents or study product from 30 days prior to Day 1 through the duration of the study.
- Other (non-pneumococcal) licensed vaccines from 30 days prior to Day 1 through Day 29.
- Blood or blood product (including IGIV) from 90 days prior to Day 1 through the duration of the study.
- Systemic immunosuppressant therapy (eg, chemotherapeutics) and immunostimulants.

- Immunomodulatory medications (eg, oral corticosteroids) from 30 days prior to Day 1 or received systemic corticosteroids exceeding physiologic replacement doses within 14 days prior to study vaccination through Day 29.

The history of all prohibited medications at any time during study participation (regardless of association with an AE) will be collected.

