### 6.1 Scheduled Study Visits

#### 6.1.1 Screening (-30 days to Day 1)

The following will take place during the visit, which will occur within 30 days prior to Day 1:

- Informed consent
- Demographics
- Review of eligibility criteria
- Medical history
- Physical exam
- Vital signs
- Biological specimen collection for clinical laboratory tests:
  - Blood for hematology and chemistry
  - Serum for infectious disease screening
  - Serum for HCG pregnancy test (for females of childbearing potential)
  - Urine for urinalysis
- Prior and concomitant medications

#### 6.1.2 Day 1

The following will take place during the visit and *prior* to study vaccine administration:

- Updated medical history
- Confirmation Inclusion/Exclusion criteria are met
- Targeted physical examination, if indicated by updated medical history
- Vital signs
- Biological specimen collection (pre-dose) for clinical laboratory tests:
  - Serum samples for immunogenicity (subjects aged 50 to 64 years)
  - [REDACTED]

- Urine pregnancy test (females of childbearing potential)
- Prior and concomitant medications
- Randomization

All eligible, consented, and randomized subjects will be vaccinated at the Day 1 Baseline visit.

- Study vaccine administration, either VAX-24 or PCV20

The following will take place during the visit and *after* study vaccine administration:

- Acute observation for at least 30 minutes after vaccine administration
- Vital signs collected at least 30 minutes after vaccine administration
- AE (solicited and unsolicited) and SAE evaluation
- Concomitant medications
- Instructions on completion of an electronic diary, use of a ruler and thermometer

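### Exclusion criterion 14 has its corticosteroid washout inequality reversed, contrary to Protocol Sections 5.2 and 5.14; it is wrong as written, with small practical effect

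*Protocol*

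**What the plan says.** Three places in the protocol set a time limit on corticosteroid use before vaccination.

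- **Section 3.4.2, criterion 14.** Meeting a listed criterion bars enrollment. This one applies to a subject who had systemic corticosteroids for at least 14 "consecutive days and has not completed treatment" 30 days or less before enrollment.
- **Section 5.2, Re-screening.** This section describes the exclusion as one for taking "medications (ie, systemic corticosteroid) within 30 days" before Day 1, and says such a subject "may be re-screened after the appropriate duration has passed".
- **Section 5.14.** Under the lead-in "Subjects must not have received or be planning to receive", it lists "Immunomodulatory medications (eg, oral corticosteroids) from 30 days prior to Day 1 or received systemic corticosteroids exceeding physiologic replacement doses within 14 days" before vaccination, with the restriction running through Day 29.

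The numbered criteria are operative. Section 3.2 defines the population as adults "who meet the eligibility criteria listed in" Section 3.4, and the Day 1 procedures in Section 6.1.2 include "Confirmation Inclusion/Exclusion criteria are met".

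**The concern.** A washout criterion should keep out subjects treated recently and let in those whose treatment ended long enough ago. Criterion 14 combines a negation with a ≤ sign, and together they reverse that. As worded, having finished within the last 30 days is what releases a subject from the exclusion, and having finished earlier is what triggers it.

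At stake is whether sites have one consistent eligibility rule. A site that follows the list literally could pass a recent long course on this criterion and turn away a subject who is properly washed out. Both outcomes contradict other sections of the same protocol.

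**Working it through.** This is a check of logic; the plan gives no figure to reproduce.

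**Inputs.** Let L be the length of the course in days and d the number of days from the end of the course to enrollment. Enrollment is taken as Day 1, because Section 5.8 defines it as randomization and Section 6.1.2 places randomization on Day 1. The 14-day and 30-day limits come from criterion 14, and the 30-day rule for comparison comes from Section 5.2.

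**What ≤ 30 days prior means.** Criterion 16 in the same list puts ≤ before 5 years to mean malignancy within the last 5 years. Read the same way, ≤ 30 days prior means within the last 30 days, or d ≤ 30.

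**Rules.**

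- As written: excluded if L ≥ 14 and not (completed with d ≤ 30), that is, if L ≥ 14 and the course is ongoing or d > 30.
- Section 5.2: excluded if the course is ongoing or d ≤ 30; may return afterwards.
- Corrected: excluded if L ≥ 14 and not (completed with d > 30), that is, if L ≥ 14 and the course is ongoing or d ≤ 30.

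**Results for a course of at least 14 days.**

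| Status at enrollment | Criterion 14 as written | Section 5.2 rule | Criterion 14 with > 30 |
|---|---|---|---|
| Ongoing | excluded | excluded | excluded |
| Ended 0 days before | not excluded | excluded | excluded |
| Ended 10 days before | not excluded | excluded | excluded |
| Ended 30 days before | not excluded | excluded | excluded |
| Ended 31 days before | excluded | eligible | not excluded |
| Ended 60 days before | excluded | eligible | not excluded |
| Ended 365 days before | excluded | eligible | not excluded |

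As written, the criterion agrees with Section 5.2 only for ongoing treatment; for every completed course of this length the answers are opposite. With > 30 they agree in every row.

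**Day 30.** Changing the sign to ≥ 30 instead would leave d = 30 not excluded. Section 5.2 covers use within 30 days and Section 5.14 starts its oral-corticosteroid prohibition at 30 days before Day 1, so both take in day 30. Only > 30 matches them.

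**The case against.** The strongest reply is that this is an editorial slip with no consequence for the trial. Much of that stands. Section 5.2 states the intended direction, and investigators are bound by the whole protocol. Section 5.14 prohibits recent oral or supraphysiologic use whether or not criterion 14 repeats it. Protocol Section 9.4 and SAP Section 4.1 remove recipients of prohibited medication from the Immunogenicity Evaluable Population. Wrongly barring a washed-out subject would require a site to apply a clinically odd reading to treatment that ended before the 30-day medication look-back in Sections 5.3 and 5.13. What the reply does not do is make the criterion correct: it is part of the list sites confirm on Day 1, and it gives the wrong answer.

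Three stronger readings are tempting, and the documents do not support them.

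- **That nobody with a completed long course can ever be enrolled.** A reader might combine literal criterion 14, which bars after day 30, with the Section 5.2 wait up to day 30 and the limit "A subject may be re-screened one time only". That mixes two readings. The Section 5.2 provision is for a subject who meets an exclusion criterion. Under the literal text, a subject 10 days off treatment does not meet criterion 14, so criterion 14 gives Section 5.2 no wait to impose.
- **That criterion 14 must also absorb the short-course limits of Section 5.14.** Courses under 14 days fall outside criterion 14 on any reading, and the inversion does not affect them. Section 5.14 is a standing prohibition that already covers use before Day 1, so it binds without being repeated.
- **That the share of days on which the two rules disagree measures the size of the problem.** Over any window chosen, such a count only restates that an inequality points the wrong way. It says nothing about how many subjects are affected.

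**Conclusion.** The concern holds as a wording error in an operative rule: criterion 14 is wrong as written. It fails to exclude a course of at least 14 days that ended within 30 days of enrollment, and it excludes one that ended earlier, contrary to Sections 5.2 and 5.14.

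The practical effect is small. Other provisions restrict recent use and the intent can be inferred. The documents give no rate of corticosteroid use, so no number of affected subjects can be stated and none is assumed. A reader might infer biased results or lost power; nothing in the documents supports that, and no sample-size, power or analysis figure depends on this criterion.

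The conclusion assumes that the ≤ sign was read correctly from the PDF. The neighbouring signs in criteria 14 and 16 (≥ 14 days, ≤ 5 years) make sense as they stand, so a reading error is unlikely.

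**What to change.** In criterion 14, replace ≤ with > before 30 days and leave the rest of the sentence alone. The criterion then excludes a subject with a course of 14 or more consecutive days unless that course ended more than 30 days before enrollment.

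Sections 5.2 and 5.14 and the SAP need no change. The cost is one symbol in the protocol text. No new data are needed, because medications in the 30 days before Day 1 are already collected.

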## 4 STUDY VACCINE

### 4.1 Investigational Vaccine (VAX-24)

VAX-24 is the Sponsor's research name for a Pneumococcal Conjugate Vaccine. VAX-24 consists of capsular polysaccharide antigens of *Streptococcus pneumoniae* (*S. pneumoniae*) serotypes 1, 2, 3, 4, 5, 6A, 6B, 7F, 8, 9N, 9V, 10A, 11A, 12F, 14, 15B, 17F, 18C, 19A, 19F, 20B, 22F, 23F, and 33F, with each of the 24 polysaccharides (one from each serotype) individually conjugated in a site-specific manner to a proprietary non-toxic diphtheria carrier protein referred to as eCRM, and mixed with ALPO.

[REDACTED]

Each vial is filled to deliver a single 0.5 mL (extractable volume) dose of VAX-24 vaccine for IM administration, with no preservative. VAX-24 is manufactured by Laboratoire Baccinex (Switzerland) and will be supplied at three strengths in single-use 2 mL glass vials. The vial is sealed with a 13 mm gray bromo butyl rubber stopper with FluroTec® coating on the side in contact with VAX-24 DP. The stopper is capped with a 13 mm crimped aluminum seal with a flip-off white cap for Low strength, a blue cap for Mid strength, and a green cap for the Mixed strength.

The three different strengths of VAX-24 will be identified as:

- Low, 1.1 mcg of Total PS/dose per serotype
- Mid, 2.2 mcg of Total PS/dose per serotype
- Mixed, 2.2 or 4.4 mcg of Total PS/dose per serotype. Conjugate Drug Substance serotypes 3, 6B, 7F, 9V, 18C, 19A, and 19F are present at the higher level, with the other 17 serotypes present at the lower level.

The vaccine must be stored in a temperature-controlled refrigerator at 2°C to 8°C with controlled, limited access, and accessible to authorized personnel only. The temperature should be monitored by checking and recording current and maximum/minimum temperature readings inside the vaccine storage unit at least once each working day.

#### 4.1.1 Active Comparator

Prevnr 20™ (PCV20), 20-valent pneumococcal conjugate vaccine is a sterile suspension of saccharides of the capsular antigens of *S. pneumoniae* serotypes 1, 3, 4, 5, 6A, 6B, 7F, 8, 9V, 10A, 11A, 12F, 14, 15B, 18C, 19A, 19F, 22F, 23F, and 33F individually linked to non-toxic diphtheria CRM197 protein. PCV20 is manufactured by Wyeth Pharmaceuticals, LLC (subsidiary of Pfizer Inc.) and is commercially available in the US. Each 0.5 mL dose of the vaccine is formulated to contain approximately 2.2 mcg of each *S. pneumoniae* serotypes 1, 3, 4, 5, 6A, 7F, 8, 9V, 10A, 11A, 12F, 14, 15B, 18C, 19A, 19F, 22F, 23F, and 33F; 4.4 mcg of the

[REDACTED]

polysaccharide from serotype 6B; 51 mcg CRM197 carrier protein; and 100 mcg polysorbate 80, 295 mcg succinate buffer, 4.4 mg sodium chloride, and 125 mcg aluminum as aluminum phosphate adjuvant. PCV20 pre-filled syringe (PFS) are to be stored at 2°C to 8°C (36°F to 46°F), as required by the manufacturer.

Refer to PCV20 Package Insert for clinical dosage and administration, storage and handling, contraindications, warnings and precautions, and summary of clinical trial results.

#### 4.1.2 Other Supplies

The following supplies are provided by the Sponsor for preparation and administration of study vaccine:

- 1 mL BD Luer-Lok™ Syringe sterile, single use polycarbonate
- 25 Gauge BD™ Needle 1 inch single use, sterile
- 25 Gauge BD™ Needle 1 1/2 inch single use, sterile

#### 4.2 Dose Preparation of Study Vaccines

A central supply depot will provide study vaccines and ancillary supplies.

Unblinded site personnel will manage all aspects of the vaccine inventory; prepare the vaccine for administration; administer the vaccine and active comparator to study subjects; and store and monitor the vaccine in a secure area and maintain all accountability documentation. All study site personnel who complete subject assessments will be blinded to the vaccines being administered to study subjects. Unblinded site personnel will be trained in all aspects of vaccine management, preparation, and administration, and will be provided a Pharmacy Manual regarding such procedures.

All study vaccines are parenteral drug products that should be inspected visually for particulate matter and discoloration prior to administration. The product should not be used if particulate matter or discoloration is found. VAX-24 and PCV20 are suspensions containing ALPO and should be shaken vigorously immediately prior to use to obtain a homogenous, white suspension in the vaccine container. The vaccines should not be used if they cannot be resuspended.

All VAX-24 doses are to be withdrawn into Sponsor-provided syringes using sterile technique. No dilution or reconstitution is necessary. VAX-24 vial must be brought to room temperature and administered  $\geq$  10 minutes and  $\leq$  60 minutes. Once VAX-24 is withdrawn into a syringe, the dose must be administered within  $\leq$  60 minutes. Detailed instructions on packaging, preparation, administration, and accountability are found in the VAX24-101 Pharmacy Manual.

PCV20 will be supplied to the clinical sites as single-use PFS packaged by the manufacturer. PCV20 should be administered by IM injection as soon as possible after being removed from

refrigeration. Preparation and administration instructions are found in the PCV20 Prescribing Information (manufacturer's package insert) and should be adhered to.

Each vaccine is administered IM in the deltoid muscle of the upper arm as a single dose of VAX-24 or PCV20.

#### **4.3 Accountability Procedures for Study Vaccines**

It is the responsibility of the Investigator to supervise accurate monitoring of the receipt, storage, dispensing and accounting of all study material according to accepted industry practice. Sites must maintain and retain accurate, original site records of study material inventory as well as copies of all invoices of study material shipments and records of study material distribution.

Drug accountability information will be collected in electronic source document format for tracking study vaccines (eg, date material was received, dispensed to individual subjects, and amount used and unused on site etc).

Each site must keep all used and unused study material until the unblinded CRA has performed vaccine accountability and arranges return to the central repository vendor or gives instruction for used vaccine disposal. Expired vaccine should be separately quarantined until the unblinded CRA has completed accountability monitoring.

Shipment of vaccine will be contingent on enrollment at the study sites. Detailed instructions on packaging, preparation, administration, and accountability are found in the VAX24-101 Pharmacy Manual.

## 5 STUDY PROCEDURES

Source documents and source data will be captured electronically, meeting the same elements of data quality and integrity (ALCOA: attributable, legible, contemporaneous, original, and accurate) as paper records. Data will be collected into a fully validated system, with changes to data captured by automatic audit trail. The clinical trial site will use their own tablets or laptops to directly record subject data and clinical observations into electronic forms. Designated site staff will receive access to the system after appropriate training. As the trial uses electronic source documents as the original point of data capture, there is no additional data transcription step for the site to enter the CRF data into the application, except for the signed informed consent form (ICF).

Some data may be captured via paper and subsequently transcribed into the eSource system. These source data will be verified by the clinical research associate and the location of the source data (ie, paper, local electronic system, etc) documented before the start of the trial. Copies of the paper source records will be uploaded into the eSource system for real-time access.

Remote monitoring of original electronic source records will be performed, but on-site monitoring would occur for review of any paper source documents and their transcription into the system, etc.

### 5.1 Informed Consent

The Investigator must obtain informed consent from study subjects at the Screening visit prior to starting any study-related activities. All prospective subjects must sign and date an Institutional Review Board (IRB)-approved ICF. For further details on informed consent, refer to [Section 10.3](#).

### 5.2 Screening

Screening procedures are listed in the Schedule of Events ([APPENDIX A](#)).

Upon entry of a subject into the Screening Form within the electronic data capture (EDC) system, each Subject will be automatically assigned a unique Subject identifier. This Subject ID will be in the following format:

Each subject who signs an ICF will receive a sequential three-digit identification number unique to the site (eg, 001, 002...). When screening information is subsequently entered into the EDC, each subject will be assigned a subject identification number with the following format:

VAX24-101 — two-digit site number — three-digit identification number

An example of a subject identification number is: VAX24-101 – 01 – 001. Subject numbers will also be sequential since screen-failed subjects will be entered into the EDC system.

[REDACTED]

Each site is required to record the reason(s) for screen failure for all subjects who receive a subject identification number within the EDC system. Sites may elect to use a pre-screening consent form, and maintain a pre-screening log for those subjects contacted for the study and will provide that log to the Sponsor or designee upon request.

#### Re-screening

A subject who meets exclusion criterion of having a current acute febrile illness at the time of scheduled enrollment may be re-screened after resolution of the acute illness. A subject who meets exclusion criteria of taking an investigational product, licensed vaccines, or medications (ie, systemic corticosteroid) within 30 days (or blood or blood product within 90 days) prior to Day 1 may be re-screened after the appropriate duration has passed. If an eligible subject is not able to be randomized and treated within 30 days of the Screening period, all screening procedures must be conducted again, including re-consenting and use of a new subject ID number. A subject may be re-screened one time only. Re-screening is not otherwise permitted.

If a subject is re-screened, a new subject number will be assigned as they are entered into the EDC for a new Screening visit and the previous subject number will be captured in the source file of the newly assigned subject number.

